Based on patient scheduling, there are approximately 4-6 new patients every week who would be a potential Patient. We will need to recruit 50% of those potential Patients over a 6-month course.

It will only be those doctors (residents) and research assistants listed on the study involved in recruiting patients. Once COVID is over, we will have research assistant involvement outside of residents and will make an addendum to the application to include them in the future.

Our facilities will offer tablets which Participants can use to answer surveys. The tablets are approved by HUMC Hospital Admin for use in clinic. The tablets belong

Patient reported outcomes from patients seen in virtual phone visits compared to in-person physical visits for post-operative follow-up at a sports medicine clinic: a prospective randomized controlled trial

to HUMC and the IT department will help us set them up. The tablets will be secured in the physician work area under lock and key.

The facilities staff will be notified that this study is taking place, so that if a Participant contacts the staff about the study, they know who to redirect and call.

The surveys are to be completed by all participants of the study. Surveys are on REDCaps hosted by Lundquist (<https://research.lundquist.org/redcap/surveys/?s=NK3YH4NWL3>) and are done online. This study will deliver the surveys in the same manner to participants that attend in-person visits and virtual visits. REDCaps will allow us to collect participants' clinical data. The REDCap administrator is aware that these surveys are collected for research purposes. The surveys will result in a score. This score from REDCaps will be part of the DHS medical record. Any Participant that is part of the study and present for an in-person post-operative appointment will receive a tablet to complete the survey after their appointment. Any Participant in the virtual phone group will receive an email with the survey to complete after attending a virtual phone visit or if the Participant is having difficulty, one of the research staff go through the questions with the Participant over the phone.

8) Prior Approvals

No prior approvals are needed for this study.

9) Study Design

a) Recruitment Methods

When: Participants will be recruited at the pre-op visit, day of surgery, or in-person 2-week post-operative visit.

Where: The Participant will be recruited at Harbor-UCLA Medical Center in-person.

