The study will be ongoing until the appropriate number of Participants are recruited from this site.

The duration of an individual Participant's participation in the study will be from initial visit where consent is asked until completion and submission of the surveys at their 6-month post-operative appointment.

The duration anticipated to enroll all study Participants will be 6 months.

The estimated date for the investigators to complete this study (complete primary analyses) is December 2023.

f) Study Endpoints

Primary study endpoints: Participant reported outcome scores through PROMIS Global.

Patient reported outcomes from patients seen in virtual phone visits compared to in-person physical visits for post-operative follow-up at a sports medicine clinic: a prospective randomized controlled trial

Secondary study endpoints: Patient survey scores for knee injuries via KOOS, and shoulder and elbow injuries via QuickDash. Patient appointment satisfaction scores will be surveyed.

g) Procedures Involved in the Human Research

There are no procedures performed.

The mentioned above surveys will be attached to this document.

Study Design:

In this prospective study, we will enroll patients undergoing operative intervention at a Sports Medicine clinic.

The patient will arrive at the 2 week post-operative appointment to sign the consent form in the presence of study team member and a witness in order to be eligible to participate in the study.

After consent is obtained, the Participant will be randomized to either in-person follow up or virtual phone follow up to take place after the 2-week post-op visit. The virtual visits will occur using the same platforms that they are currently taking place in accordance and required by LA County DHS/HUMC.

The randomization process will utilize block randomization and be conducted by an online program called <http://www.randomization.com>. (Wichmann and Hill, 1982, as modified by McLeod, 1985). The Participant will be assigned a number based on the order the Participant is enrolled in the study and that number will be randomly assigned to a follow-up group based on that number.

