The Participant will be notified at the 2-week post-op or after if they will receive in-person follow up or virtual phone follow-up. If the Participant in the virtual phone group feel they need an in-person visit, the Participant will be free to make an in-person follow-up. After each follow up visit (6-week, 12-week, and 6-month), the Participant will be asked to fill out 30-minute surveys.

The surveys the Participant will be asked to fill out are the following:

1. KOOS- a knee specific survey
2. Quick Dash Outcome Measure
3. PROMIS Global
4. General Health Questionnaires (2)
5. Patient Satisfaction Survey -We will have the patient complete this also after every visit to see if their preferences change over time as their recovery changes.

If a Participant attends an in-person post-operative follow up visit, then the study team member will check to see if the participant is on the in-person list. If the participant is on the list, then he or she will be given a tablet to fill out the online survey after the appointment. The tablet will be set up so a link to the surveys can be accessed and participants can fill out the surveys. The surveys are on REDCaps (<https://research.lundquist.org/redcap/surveys/?s=NK3YH4NWL3>). Patients will be able to fill out the survey at home. For Participants that attend a virtual appointment, an online

Patient reported outcomes from patients seen in virtual phone visits compared to in-person physical visits for post-operative follow-up at a sports medicine clinic: a prospective randomized controlled trial

link to the survey on REDCap will be sent to the Participant's email. Members of the study team can also call the participant to conduct the survey over the phone. The emails will be made secure by having them sent out from an official DHS email that uses Microsoft outlook and requires double verification to logon. The content of the email message is included in the IRB submission as a separate document.

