The procedure for orderly termination is that the Participant will notify any staff member including nurses or providers. The study coordinator will be notified and the Participant's name, MRN, and email will be removed from the data list.

The Participant's survey responses will be linked to Patient identifiers so it will be possible to eliminate the Participant's responses.

Patient reported outcomes from patients seen in virtual phone visits compared to in-person physical visits for post-operative follow-up at a sports medicine clinic: a prospective randomized controlled trial

10) Risks to Participants

Participants may feel inconvenienced having to stay 30 minutes longer to complete the survey on the tablets if you are attending an in-person visit.

Participants may also experience inconvenience or frustration if the survey system freezes and does not operate appropriately. You may also feel bored or tired.

Risk Mitigation

The exclusion criteria exclude any minors, prisoners, and adults who cannot give consent, from participating in the study.

Participants will be given the opportunity to pick a time convenient for them to answer the questionnaires after the virtual phone visit. Participants part of the in-person visit will answer surveys after the visit. Participants are encouraged to answer all questions. If they skip any questions or the survey is not answered completely, their survey may be removed. Participants may stop at any time. They may skip any questions they do not wish to answer, and they may stop at any time. Participants may withdraw from the study at any time. To decrease risk mitigation, the data will be kept on REDCap hosted by Lundquist. Only members of the research team will have access to the data information.

11) Potential Benefits to Participants

We cannot promise any benefits to Participants or others from taking part in this research. We cannot promise any benefits to others from taking part in this research.

The study poses no more than minimal risk with the main risk a breach of confidentiality and the study involves ensuring patient reported outcome surveys completed consistently (which is currently not done in the current clinical setting) and scoring calculated and recorded in the medical record

12) Provisions to Protect the Privacy Interests of Participants

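### Skipping a question is allowed, yet any skipped question is grounds for removing the survey, so primary-endpoint data can be excluded after randomisation with no stated rule

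*Combined protocol and SAP*

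**What the plan says.** Section 10 (Risk Mitigation) contains two statements that pull against each other. Participants are told: "They may skip any questions they do not wish to answer, and they may stop at any time". The same paragraph says: "If they skip any questions or the survey is not answered completely, their survey may be removed". The trigger is a single skipped question. Nothing states who decides, when, on what threshold, or whether the decision is made without knowledge of study arm.

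The rule acts on the main outcome. Section 9(f) states: "Primary study endpoints: Participant reported outcome scores through PROMIS Global". Section 9(g) says that after consent "the Participant will be randomized to either in-person follow up or virtual phone follow up to take place after the 2-week post-op visit", and then: "After each follow up visit (6-week, 12-week, and 6-month), the Participant will be asked to fill out 30-minute surveys". Every outcome survey is therefore completed after allocation.

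Collection differs by arm. Under section 7, a participant at an in-person visit "will receive a tablet to complete the survey after their appointment". A participant in the virtual arm is emailed the survey or, if that proves difficult, "one of the research staff go through the questions with the Participant over the phone".

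Section 9(i) plans a Student t-test at each visit, a chi-squared test for visit preference and an analysis of variance for satisfaction over time. It defines no analysis population, no scoring rule for partly answered instruments and no handling of missing data.

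**The concern.** Participants are allowed to do something that then makes their data removable, and the choice to remove is left open. Under a literal application, an instrument that could still be scored can be discarded because of one blank. If a survey means everything completed at a visit, a complete PROMIS Global can be lost because of a blank in a different questionnaire.

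Randomisation makes the two arms comparable as allocated. An exclusion that depends on what participants do afterwards can undo that. Two conditions are needed for bias: skipping or removal must differ between arms, and it must be related to outcome. The different collection modes make the first plausible. The second is plausible because people who are recovering poorly may answer less fully. Neither is shown by the documents, but the rule does nothing to guard against either.

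**Working it through.** **Inputs from the documents.** Two-group comparison, alpha 0.05, power 80%, standardised effect 0.8, 26 per group and 52 in total (sections 9(c) and 9(i)); recruitment target of at least 104, to leave room for removals and losses (section 9(c)); t-test at each visit (section 9(i)). Sidedness is not stated; two-sided is taken from the hypothesis of a difference.

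**Step 1: reproduce the plan's figure.** The two-sided t-test (noncentral t) at effect 0.8 needs 25.52 per group, rounded up to 26. Power at 26 is 80.7%. The stated figure reproduces.

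**Step 2: what removal does to power.** With 104 recruited there are 104 / 2 = 52 per arm. At effect 0.8:

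| Share of surveys lost | Left per arm | Power |
|---|---|---|
| 0% | 52 | 98.1% |
| 20% | 41.6 | 95.0% |
| 30% | 36.4 | 92.0% |
| 50% | 26 | 80.7% |

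If the target is met, planned power survives a loss of half the surveys. Dropout draws on the same allowance.

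**Step 3: how many surveys one blank could expose.** The documents give neither item counts nor skip rates, so both are assumed here. If each of k items is skipped independently with probability q, the share of surveys with at least one blank is 1 − (1 − q)^k.

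| Items assumed | q = 0.5% | q = 1% | q = 2% |
|---|---|---|---|
| 10 (one instrument) | 4.9% | 9.6% | 18.3% |
| 40 (a visit package) | 18.2% | 33.1% | 55.4% |

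These are the shares eligible for removal. The text says only that they may be removed, so actual loss could be smaller. The gap between the rows shows how much depends on the undefined word survey.

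**Step 4: bias.** Let a fraction f of an arm's surveys be removed, and let those respondents score g SD below the ones retained, whose mean is R. The full-arm mean is (1 − f)R + f(R − g) = R − fg, so the retained mean is too high by f × g. The spurious difference between arms is the difference in f × g. The values of f and g are assumptions.

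- 20% removed in one arm, none in the other, g = 0.5: 0.20 × 0.5 = **0.10 SD**.
- 20% against 5%: (0.20 − 0.05) × 0.5 = 0.075 SD; with g = 1, 0.15 SD.
- 30% against 10%: (0.30 − 0.10) × 0.5 = 0.10 SD; with g = 1, 0.20 SD.
- Extreme case, normal scores, the lowest 20% removed in one arm only: φ(z) / (1 − 0.20), with z the 20th percentile of the standard normal, gives 0.35 SD.
- Equal removal in both arms with the same g: zero.

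Over-recruitment does not enter this formula. A larger sample estimates the biased difference more precisely.

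**The case against.** Much can be said for the plan, and several stronger readings do not stand.

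- **Power.** A reader might start from 26 per group and infer that losing 10%, 20% or 30% of surveys cuts power to 76.3%, 71.1% or 65.0%. But 52 is the number needed to complete, and section 9(c) aims for at least 104. The power argument falls away if that target is met.
- **Whole-package removal.** A reader might infer that one blank always discards everything from that visit. Section 9(g) lists the instruments individually as surveys, and section 9(i) refers to a total score for each, which favours the narrow reading. Section 9(g) also describes successive pages of one survey, which favours the wide one. The text is ambiguous. Even the narrow reading drops an instrument for a single blank, whether or not it can be scored.
- **Unblinded selection.** A reader might infer that staff choose removals after seeing arm and answers. The documents do not say so. Section 9(j) makes the list showing each participant's group available to the research team, but says it holds no health information, and section 9(i) removes identifiers at export. That does not establish masking to arm; the process is simply unspecified.
- **Irrecoverable data.** Removal may mean exclusion from analysis and not deletion. Responses are held in REDCap, scores enter the medical record (section 7), and data are stored for 3 years (section 9(i)).
- **Differential completeness.** Section 7 says both groups receive the surveys in the same way, and section 9(g) allows completion at home. The modes actually described still differ, but neither the direction nor the size of any difference is documented. The 0.10 SD illustration is one-eighth of the 0.8 design effect (0.10 / 0.8).

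What remains is an operative removal sentence with no objective criterion, and nothing in section 9(i) that replaces it.

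**Conclusion.** The concern holds in a limited form. Sections 10 and 9(i) together leave a discretionary exclusion of primary-endpoint surveys after randomisation, triggered by behaviour the protocol permits. It can discard valid data, and it can bias the comparison if skipping or removal differs by arm and is related to outcome.

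The size cannot be taken from the documents. Under the one-arm assumption (20% removed, 0.5 SD worse) it is 0.10 SD; the other moderate scenarios give 0.075 to 0.20 SD, and the extreme case 0.35 SD. If removal is balanced and has the same relation to outcome in each arm, there is no bias. Selective loss is something the rule permits, not something shown to occur, and loss of power is not the issue. The sentence should be changed because doing so costs little and removes a discretion that serves no stated analytic purpose.

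**What to change.** Replace the removal sentence in section 10, and add to section 9(i):

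> Apart from responses eliminated because a participant withdraws, no survey is excluded because questions were skipped. Each instrument is assessed separately and kept at that visit whenever it can be scored from the answered items under its scoring rules, regardless of blanks in other instruments and without reference to study arm. An instrument that cannot be scored is treated as missing at that visit, and the number missing is reported by arm and visit. Each visit's comparison includes every randomised participant with a scorable instrument at that visit, in the group to which they were randomised.

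The opening exception keeps the text consistent with section 9(l), which allows a withdrawing participant's responses to be eliminated. The last sentence fits the separate t-test at each visit: someone with only a 6-week score contributes at 6 weeks and not at 6 months. The change does not deal with surveys that are never returned or cannot be scored; the counts by arm and visit make that loss visible.

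The cost is slightly more scoring and reporting work, with no added patients or visits.
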